## 5.4. Other Efficacy Variable(s)

The exploratory efficacy endpoints are:

- Failure free survival (FFS)
- Overall survival (OS)
- Number and proportion of subjects with all immunosuppressants withdrawn
- Best organ response rate

### 5.4.1. Definition

#### Failure free survival (FFS):

Failure free survival (FFS) is defined as the duration from the date of initial dose to the date of relapse of malignancy, initiation of new immunosuppressive therapy for GVHD or death, whichever occurs first. FFS will be right censored based on [Table 4](#).

**Table 4: Date of Event or Censoring for Failure Free Survival**

Situation	Date of FFS event or Censoring	Outcome
Death	Date of death	Event
New subsequent cGVHD treatment	Date of starting the new subsequent cGVHD treatment	Event
Relapse of malignancy	Start date of relapse of malignancy	Event
Not known to have event at the data analysis cutoff date (this includes subjects who were known to have event after the data analysis cutoff date)	Date of last known date (last visit) showing no evidence of event.	Censored

**Overall survival (OS):**

Overall survival (OS) is defined as the duration from the date of initial dose to the date of the subject's death. OS will be right censored if no death has occurred at the data analysis cutoff date.

**Best organ response rate:**

Best organ response rate is defined as the proportion of responders (CR or PR) in a specific organ or site. Skin, mouth, liver, upper GI, lower GI, esophagus, lung, eye, and joint/fascia are the organs or sites considered.

**5.4.2. Analysis Methods**

The Kaplan-Meier method will be used to descriptively summarize the FFS. Median FFS and the corresponding 95% confidence interval will be provided if estimable with Kaplan-Meier plot.

The OS will be evaluated in the same manner as FFS.

Number and proportion of subjects with all immunosuppressants withdrawn and organ response will be summarized by descriptive statistics.

**6. SAFETY**

Unless specified otherwise, all safety analyses will be based on Safety Analysis Set.

**6.1. Adverse Events**

The verbatim terms used in the CRF by investigators to identify adverse events will be coded using the Medical Dictionary for Regulatory Activities (MedDRA). Adverse events will be graded by the investigator according the National Cancer Institute common terminology criteria for adverse events (CTCAE) Version 4.03. Any AE occurring at or after the initial administration of study agent through the day of last dose plus 30 days or initiation of subsequent cGVHD therapy is considered to be treatment-emergent. If the event date is recorded as partial or completely missing, then the event will be considered to be treatment-emergent unless it is known to be prior to the first administration of study agent based on partial onset date or resolution date. If the event is study drug-related regardless of the start date of the event, it is considered to be treatment-emergent. If an event that is present at baseline but worsens in severity or is subsequently considered drug-related by the investigator, then it is considered to be treatment-emergent. All reported treatment-emergent adverse events will be included in the analysis. For each adverse event, the number and percentage of subjects who experience at least 1 occurrence of the given event will be summarized.

Summary tables will be provided for:

- Overall summary of all treatment-emergent AEs(TEAEs)
- TEAEs by System Organ Class (SOC), preferred term (PT) and toxicity Grade 3 or higher
- TEAE with frequency of at least 10% by SOC, PT and toxicity Grade 3 or higher
- Drug-related TEAEs by SOC, PT and toxicity Grade 3 or higher

- Serious TEAEs by SOC, PT and toxicity Grade 3 or higher
- TEAEs leading to dose reduction by SOC, PT and toxicity Grade 3 or higher
- TEAEs leading to discontinuation of study drug by SOC, PT and toxicity Grade 3 or higher
- Fatal TE AEs by SOC and PT
- TEAEs by SOC, PT and toxicity by period

In addition to the summary tables, listings will be provided for subjects who:

- Had any AE
- Had SAEs
- Had TEAEs leading to dose modification
- Had TEAEs leading to discontinuation of study drug
- Had drug-related TEAEs
- Had Fatal TEAEs

Incidence of treatment-emergent adverse events of special interest will be summarized.

### **6.1.1. AEs of special interest (AESI)**

Number and percent of subjects with following AESIs will be summarized by preferred terms.

#### **Major hemorrhage**

Major hemorrhage is defined as:

- Treatment-emergent hemorrhagic adverse event of Grade 3 or higher. All hemorrhagic events requiring a transfusion of red blood cells should be reported as Grade 3 or higher adverse events per NCI-CTCAE.
- Treatment-emergent SAE of Hemorrhagic event of any grade
- Treatment-emergent central nervous system hemorrhage/hematoma of any grade

#### **Hemorrhagic event**

Hemorrhagic events will be identified by hemorrhage Standardized MedDRA Query [SMQ] excluding laboratory terms.

#### **Cardiac arrhythmia**

Cardiac arrhythmia will be determined based on Cardiac arrhythmias (SMQ, broad and narrow).

#### **Interstitial Lung Disease**

Interstitial Lung Disease (ILD) will be determined based on Interstitial lung disease (SMQ, narrow). All treatment emergent ILD events will be summarized by preferred terms.

## **Severe Cutaneous Adverse Reaction**

Severe Cutaneous Adverse Reaction (SCAR) will be determined based on Severe cutaneous adverse reactions (SMQ, narrow).

## **Hypertension**

Hypertension will be determined based on Hypertension (SMQ, narrow).

## **Other Malignancies**

Treatment-emergent Neoplasms benign, malignant and unspecified (incl cysts and polyps) of any grade (SOC). Relapse of underlying malignancy will not be considered as other malignancies.

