11.7. Safety Analyses

Safety population will be used for safety analyses. The safety parameters to be evaluated are the incidence, intensity, relationship to study drug, action taken with regards to the study drug, and type of adverse events, vital signs measurements, and clinical laboratory results in the safety population. Exposure to and reasons for discontinuation from study treatment will be tabulated in the all treated population.

Adverse Events

The verbatim terms used in the CRF by investigators to identify adverse events will be coded using the Medical Dictionary for Regulatory Activities (MedDRA). All reported adverse events will be included in the analysis. Treatment-emergent adverse events are adverse events with onset during the treatment phase or that are a consequence of a preexisting condition that has worsened since baseline, and occur during treatment or within 30 days following the last dose of study treatment, or any adverse event that is considered study treatment-related regardless of the start date of the event. The number and percent of subjects with treatment-emergent adverse events will be summarized according to intensity using the NCI-CTCAE (Version 4.03), drug relationship, and outcome. For each adverse event, the percentage of subjects who experience at least 1 occurrence of the given event will be summarized. Summaries, listings, datasets, or

subject narratives may be provided, as appropriate, for those subjects who die, who discontinue study drug due to an adverse event, or who experience a severe or an SAE.

Clinical Laboratory Tests

Laboratory data will be summarized by type of laboratory test. Reference ranges and markedly abnormal results (specified in the Statistical Analysis Plan) will be used in the summary of laboratory data. Descriptive statistics will be calculated for each laboratory analyte at baseline and for observed values and changes from baseline at each scheduled timepoint. Frequency tabulations of the changes from baseline results will be presented in pre versus postintervention cross-tabulations (with classes for below, within, and above normal ranges). Frequency tabulations of the abnormalities will be made. A listing of subjects with any laboratory results outside the reference ranges will be provided. A listing of subjects with any markedly abnormal laboratory results will also be provided.

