12.3.4. Other Malignancies

In addition to all routine adverse event reporting; all new malignant tumors, including solid tumors, skin malignancies, and hematologic malignancies; are to be reported for the duration of study treatment and during any protocol-specified follow-up periods including postprogression follow up for overall survival.

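### The SAP's Other Malignancies category counts benign neoplasms, and late unrelated malignancies that the protocol collects appear in no summary table

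*SAP*

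**What the plan says.** SAP 6.1.1, under Other Malignancies, sets the category as "Treatment-emergent Neoplasms benign, malignant and unspecified (incl cysts and polyps) of any grade (SOC". The one stated exclusion is relapse of the underlying malignancy. AESIs are displayed as number and percent of subjects by preferred term.

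SAP 6.1 decides which events reach the tables: "All reported treatment-emergent adverse events will be included in the analysis", and "Incidence of treatment-emergent adverse events of special interest will be summarized". An event starting from first dose "through the day of last dose plus 30 days or initiation of subsequent cGVHD therapy is considered to be treatment-emergent". There are three exceptions:

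- Related events: "If the event is study drug-related regardless of the start date of the event, it is considered to be treatment-emergent".
- Events with a partial or missing date count unless they are known to precede first dose.
- A condition present at baseline counts if it worsens or is later judged drug-related.

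The protocol is narrower on event type and wider on time. Section 12.3.4 says: "In addition to all routine adverse event reporting; all new malignant tumors, including solid tumors, skin malignancies, and hematologic malignancies; are to be reported", both while on treatment and "during any protocol-specified follow-up periods including postprogression follow up for overall survival". It sets no relatedness condition. Section 11.7 says "All reported adverse events will be included in the analysis", then plans its number-and-percent summaries for treatment-emergent events.

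For listings, SAP 6.1 plans one of subjects with any AE and one of subjects with SAEs, and SAP 6.2 and 6.5 list deaths. SAP Attachment 1 titles its general AE listing as treatment-emergent and leaves details to the Data Presentation Specifications.

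**The concern.** The category is called malignancies but is built from a system organ class that includes benign lesions, so its label and any total under it do not say what was counted. It also omits part of what the protocol set out to collect. Section 12.3.4 extends collection of new malignancies beyond the routine AE period, and the cases it adds are largely those that the treatment-emergent restriction removes from the tables.

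Protocol 1.4.3 names nonmelanoma skin cancer as a risk seen with ibrutinib. A reader who takes the category total as the malignancy count could therefore be looking at the wrong subjects in either direction.

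**Working it through.** The plan states no figure for this category, so there is nothing to reproduce. The check sets the definitions side by side, applies the SAP's rule to example cases, and sizes one misclassified subject.

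**Step 1: event type**

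| | Protocol 12.3.4 | SAP 6.1.1 |
|---|---|---|
| Malignant, new | yes | yes, if treatment-emergent |
| Benign, cysts, polyps | no | yes, if treatment-emergent |
| Relapse of underlying malignancy | not a new tumor | excluded |

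The other AESIs defined in SAP 6.1.1 rest on a MedDRA query or part of one; Hypersensitivity is deferred to the Data Presentation Specifications. Other Malignancies is the only one defined by a whole system organ class.

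**Step 2: time**

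The SAP does not say which of its two end points closes the window when both exist, so both readings are tested. Assumed for illustration: last dose on Day 200, and subsequent cGVHD therapy never, on Day 210 or on Day 260. Last dose plus 30 days is 200 + 30 = Day 230. The event is a new malignancy, fully dated and not drug-related.

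| Subsequent therapy | Reading | Window ends | Day 100 | Day 215 | Day 235 | Day 270 | Day 400 |
|---|---|---|---|---|---|---|---|
| none | either | 230 | in | in | out | out | out |
| Day 210 | earlier date | 210 | in | out | out | out | out |
| Day 210 | later date | 230 | in | in | out | out | out |
| Day 260 | earlier date | 230 | in | in | out | out | out |
| Day 260 | later date | 260 | in | in | in | out | out |

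Onsets on Days 270 and 400 are out in every row, so the reading moves only the start of the gap. If the same events were drug-related or incompletely dated, all would be in. The baseline-worsening exception does not apply to a new malignancy.

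The gap is built into the design. Protocol 10.2 requires study drug to stop at cGVHD progression, and Protocol 9.1.1 then follows survival and subsequent cGVHD treatment every 12 weeks. Much of the follow-up that 12.3.4 names therefore lies outside the window.

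**Step 3: where a late case would appear**

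It enters no AE or AESI summary table. A serious case goes to the SAE listing and a fatal one to the death listing. A late, non-serious, non-fatal case is listed under SAP 6.1 (any AE) but not under the Attachment 1 title (treatment-emergent only).

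**Step 4: size**

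The shift is subjects misclassified / N. N=17 is the planned sample size (SAP 1.4), and N=20 the approximate enrollment in SAP 1.2.

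- One subject: 1/17 = 5.9%; 1/20 = 5.0%.
- Two subjects (an assumption, to show the range): 2/17 = 11.8%; 2/20 = 10.0%.

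Removing benign terms lowers the count, and adding late malignancies raises it. One benign lesion counted plus one late malignancy omitted gives +1 − 1 = 0: the total is unchanged, but the wrong subject is in it.

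**The case against.** The strongest reply is that the planned display already deals with most of this. Preferred-term rows show a cyst or polyp under its own name, and with about 20 subjects a reader can separate the terms by eye. A whole-class search errs toward inclusion and keeps unspecified neoplasms that may prove malignant. Section 12.3.4 is a reporting duty and promises no table, and the protocol's own AESI section (12.3.3) defines only major hemorrhage. Protocol 11.7 also plans its summaries for treatment-emergent events, so the SAP follows its structure. Drug-related and incompletely dated late cases are counted, and many others would be listed as SAEs. A percentage from post-progression contacts, possibly by telephone and after other therapy has begun, would be hard to interpret.

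Much of this stands as a limit on importance. The preferred-term rows stay correct, the residual gap is narrow, and a listing goes a long way in so small a trial. The difference between SAP 6.1 and Attachment 1 could be abbreviation, which the unseen Data Presentation Specifications might settle.

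It does not remove the defect. Preferred-term rows do not correct the label or a total beneath it. The SAP gives this definition outright, without deferring it. Its sentence on scope adds a treatment-emergent restriction that the matching sentence in Protocol 11.7 lacks. Even if that sentence was never meant to reach cases collected only under 12.3.4, those cases still have no planned summary. The interpretation problem argues for a separate row, not for leaving the cases out.

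**Conclusion.** The concern holds. As written, the Other Malignancies count can include subjects with benign lesions only. It also leaves out any subject whose new malignancy is fully dated, not judged drug-related, and starts after the treatment-emergent window.

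Each misclassified subject moves the category rate by 5.0 to 5.9 points (N=20 to N=17). The net direction is unknown, and the documents give no expected number of such subjects. This does not mean that late malignancies go unreported: most should appear in listings. The analysis is descriptive and no success criterion depends on it, so this should be corrected but does not threaten the trial's conclusions. The definitional finding rests on the SAP text alone. Where late cases would finally be displayed is less certain, because the CRF and the Data Presentation Specifications were not available.

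**What to change.** 1. Restrict Other Malignancies to malignant-tumor terms, using a malignant-tumor MedDRA query or a reviewed preferred-term list, and keep the relapse exclusion. If benign and unspecified neoplasms are wanted, show them under their own label.
2. Add a separate row for new malignancies with onset after the treatment-emergent window through end of follow-up, whatever their relatedness. State which date closes the window. Read the row beside Time on Study (SAP 2.7), which SAP 4.3 already summarizes.
3. Give the AE listing the same scope in SAP 6.1 and Attachment 1, so that a late non-serious case is listed.

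The cost is SAP wording, one added row, one listing title and minor reprogramming. The protocol already requires these reports. The CRF should be checked to confirm that it captures them in usable form. The drawback is that late cases are harder to attribute once other cGVHD therapy has started, which is why they belong in their own row and not in the treatment-emergent count.

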## **Hypersensitivity**

This definition will be specified in DPS, separatory.

## **CNS Hemorrhage**

CNS hemorrhage is a subset of CNS related PTs in the hemorrhage SMQ.

## **Ischemic stroke**

Ischemic stroke is determined based on Ischemic central nervous system vascular conditions (SMQ).

## **Cardiac failure**

Cardiac failure is determined based on Cardiac failure SMQ (narrow).

## **6.2. Death**

Subjects who died during the study will be listed.

## **6.3. Clinical Laboratory Tests**

All clinical laboratory tests will be displayed for the subjects included in the safety analysis set. Laboratory data for hematology and serum chemistry tests will be reported in SI units. Applicable laboratory results will be graded according to NCI-CTCAE Version 4.03.

The following laboratory tests will be analyzed:

- Hematology: hemoglobin, platelet count, white blood cell (WBC) count, absolute neutrophil count (ANC), absolute lymphocyte count, and absolute eosinophil count
- Chemistry: sodium, potassium, glucose, total bilirubin, blood urea nitrogen (BUN), creatinine, total protein, aspartate aminotransferase (AST), alanine aminotransferase (ALT), alkaline phosphatase, lactic acid dehydrogenase (LDH), uric acid and albumin.
- Donor/host chimerism, serum immunoglobulin levels (IgG, IgM, IgA)

Descriptive statistics and change from baseline will be presented for all laboratory tests with continuous values at scheduled time points.

Frequency tabulations of the changes from baseline results will be presented in pre versus postintervention cross-tabulations (with classes for Low, Normal, and High). Frequency tabulations of the abnormalities will be made. A listing of subjects with laboratory results will be provided. A listing of subjects with liver function abnormality will also be provided. Parameters with predefined NCI-CTCAE toxicity grades will be summarized. Change from baseline to the worst adverse event grade experienced by the subject during the study will be provided as shift tables.

#### **6.4. Vital Signs and Physical Examination Findings**

Continuous vital sign parameters including temperature, respiratory rate, weight, pulse and blood pressure (systolic and diastolic) will be summarized at each assessment time point. A listing will also be provided.

#### **6.5. Death**

Subjects who died in the study will be listed.

#### **6.6. Other Safety Parameters**

Descriptive summary will be provided for following parameters:

- Karnofsky/Lansky Performance Scale
- Forced expiratory volume in 1 second (FEV1).

Corresponding listings will also be provided.

### **7. PHARMACOKINETICS/PHARMACODYNAMICS**

#### **7.1. Pharmacokinetics**

Pharmacokinetic evaluable analysis set will be used for PK analyses. The individual plasma concentration data of ibrutinib and PCI-45227 will be listed and graphically displayed (normal scale and semilog scale). Concentrations below the lowest quantifiable concentration or missing data will be labeled as such in the concentration data presentation. The data will be summarized at each timepoint using descriptive statistics (mean, standard deviation [SD], coefficient of variation, median, minimum and maximum) and mean ( $\pm$ SD) concentration-time profile will be graphically displayed (normal scale and semilog scale). Concentration data below the lowest quantifiable concentration will be treated as zero in the summary statistics. Subgroup analysis by concomitant CYP3A inhibitors will be performed. Additional analyses may be performed as deemed necessary.

For concentration summary, applying the following rules.

- When more than half (>50%) of concentration data are BQL at each scheduled time point, mean and median will be reported as 'BQL'; SD and %CV are reported as 'NC'; maximum and minimum will be reported as observed (including BQL).

- When number of concentration data are equal to or less than 2, SD, %CV, median, minimum and maximum will be shown as 'NC' regardless of the proportion of BQL.

The individual PK parameters ( $C_{\max}$ ,  $t_{\max}$ ,  $t_{1/2}$ ,  $t_{\text{last}}$ ,  $CL/F$ ,  $Vd_z/F$ ,  $AUC_{\text{last}}$ ,  $AUC_{24}$ ,  $AUC_{\infty}$  and  $\lambda_z$ ) of ibrutinib and PCI-45227 will be calculated using noncompartmental analysis based on actual sampling times. Accumulation ratios based on  $C_{\max}$  and  $AUC_{24}$  for Week 2 is derived for both ibrutinib and PCI-45227. Metabolite-to-parent ratio (MPR) based on  $C_{\max}$ ,  $AUC_{\text{last}}$ ,  $AUC_{24}$  and  $AUC_{\infty}$  will be generated. Dose-normalized  $C_{\max}$ ,  $AUC_{\text{last}}$ , and  $AUC_{24}$  will be calculated to a 420 mg ibrutinib dose. Individual values ( $C_{\max}$ ,  $t_{\max}$ ,  $t_{1/2}$ ,  $t_{\text{last}}$ ,  $CL/F$ ,  $Vd_z/F$ ,  $AUC_{\text{last}}$ ,  $AUC_{24}$ ,  $AUC_{\infty}$ ,  $\lambda_z$ , dose-normalized  $C_{\max}$ ,  $AUC_{\text{last}}$ , and  $AUC_{24}$ , accumulation ratios based on  $C_{\max}$ , accumulation ratio based on  $AUC_{24}$ , MPR based on  $C_{\max}$ , MPR based on  $AUC_{\text{last}}$ , MPR based on  $AUC_{24}$  and MPR based on  $AUC_{\infty}$ ) will be listed and summarized for ibrutinib and PCI-45227 using descriptive statistics (mean, SD, coefficient of variation [CV], geometric mean, median, minimum and maximum [SD, CV, geometric mean are not needed for  $t_{\max}$  and  $t_{\text{last}}$ ]).

Subgroup analysis by ibrutinib dose and concomitant CYP3A inhibitors will be performed on the individual PK parameters of ibrutinib and PCI-45227 ( $C_{\max}$ ,  $t_{\max}$ ,  $t_{1/2}$ ,  $t_{\text{last}}$ ,  $AUC_{\text{last}}$ ,  $AUC_{24}$ ,  $AUC_{\infty}$  and  $\lambda_z$ ). Only strong/moderate CYP3A inhibitors taken on the PK assessment days (Week 1, Day 1 and Week 2, Day 1) will be considered. The subgroups will be defined based on the name of the inhibitors (eg, fluconazole [ibrutinib dose: 420 mg]). Summary tables will be provided to present the summary statistics derived for each subgroup. In addition, individual and mean values of selected PK parameters (eg,  $C_{\max}$ ,  $AUC_{\text{last}}$ ) will be graphically presented to visually compare the values between each subgroup. The graphical presentation will be performed for dose-normalized PK parameters (eg, dose-normalized  $C_{\max}$ ,  $AUC_{\text{last}}$ ) regardless of ibrutinib dose.

Additional analyses may be performed as deemed necessary.

For PK parameter summary, applying the following rules.

- In the case following criteria are not met,  $t_{1/2}$ ,  $AUC_{\infty}$ ,  $CL/F$ ,  $Vd_z/F$ ,  $\lambda_z$ , and MPR based on  $AUC_{\infty}$  will be reported with annotation as such and excluded from the descriptive statistics.
  - At least 3 data points are used in calculation for  $\lambda_z$ ;
  - $r^2_{\text{adj}}$  for the regression of  $\lambda_z \geq 0.90$ ;
  - $\%AUC_{\infty, \text{ex}}$  is  $\leq 20\%$ .

Data or subjects will be excluded from the analysis if the data do not allow for accurate assessment of the PK. All subjects and samples excluded from the analysis will be clearly documented in the study report.

